## 2. INTRODUCTION

Urovant Sciences GmbH (Urovant) is developing URO-902 (formerly known as *h*Maxi-K or pVAX/*h*Slo) for the treatment of overactive bladder (OAB) and urge urinary incontinence (UII) in adults who have been inadequately managed by pharmacologic therapy.

### 2.1. Background

#### *Overactive Bladder*

[figure not shown]
OAB is highly prevalent and affects approximately 16% of the population in the United States and Europe. Prevalence increases with age, affecting approximately a third of people 75 years and older [Stewart, 2003; Milsom, 2001]. The International Continence Society (ICS) defines OAB as urgency, with or without urge incontinence, usually associated with frequency and nocturia [Abrams, 2002]. Urgency is defined as a sudden compelling desire to void which is difficult to defer and, from the medical definition perspective, it is a necessary symptom for OAB. Urgency incontinence is the involuntary loss of urine accompanied by urgency (referred to as OAB Wet) and is present in approximately one-third of patients with OAB [Stewart, 2003; Milsom, 2001]. In the absence of incontinence, OAB is referred to as OAB Dry. OAB has been shown to negatively impact both social and medical well-being and represents a significant burden in terms of annual direct and indirect healthcare expenditures [Kelleher, 2002; Abrams, 2000; Reynolds, 2016].

[figure not shown]
Currently, the predominant class of drugs used to treat OAB is antimuscarinics. The clinical utility of antimuscarinics is limited by their modest efficacy and poor tolerability due to mechanism-based side effects including dry mouth and constipation. In addition to poor tolerability and modest efficacy, a recent body of literature suggests that chronic use of anticholinergics is associated with cognitive impairment and dementia [Risacher, 2016; Gray, 2015]. Mirabegron (Myrbetriq®; Astellas Pharma US, Inc), a β3-agonist and smooth muscle relaxer, is currently approved in multiple countries for the treatment of OAB [Nitti, 2013]. The reported adverse effects with mirabegron were similar to antimuscarinics, but with a lower incidence of dry mouth compared with tolterodine, an antimuscarinic. However, the effects of mirabegron on the cardiovascular system, pharmacokinetic interactions with other drugs, and increased incidence of new malignant events will require careful evaluation in the near future [Sacco, 2012]. In addition, BOTOX® (onabotulinumtoxinA), a neurotoxin which inhibits muscle contraction by blocking neuromuscular transmission through decreased acetylcholine release, has been approved for the treatment of neurogenic and idiopathic OAB (since 2011 and 2012, respectively). BOTOX is administered via multiple intradetrusor injections into the bladder wall about every 6 months. BOTOX has been associated with urinary tract infections (UTIs), dysuria, and urinary retention. Other side effects are consistent with the mechanism of action of botulinum toxin and may include asthenia, generalized muscle weakness, diplopia, ptosis, dysphagia, dysphonia, dysarthria, urinary incontinence, and breathing

difficulties. These symptoms have been reported hours to weeks after injection [BOTOX Package Insert, 2018].

A major problem with currently available OAB treatments is that even when these drugs have documented efficacy, treatment is still limited by their side effects. There is a significant unmet need for the treatment of OAB with agents with novel mechanisms of action and a well-tolerated safety profile.

*URO-902*

## 2.2. Study Rationale

Overactive bladder is a highly prevalent disease shown to negatively impact both the social and medical well-being of patients. Many of the existing treatments are limited by their side effects. Thus, there is a significant unmet need for the treatment of OAB with agents with novel mechanisms of action and a well-tolerated safety profile, in particular, for patients who have been inadequately managed by pharmacologic therapy. URO-902 (pVAX/*hSlo*) is a GMP manufactured double-stranded DNA plasmid (pVAX vector) containing a cDNA insert encoding the pore-forming  $\alpha$  subunit of the human smooth muscle Maxi-K channel, *hSlo*. The Maxi-K channel is a prominent and well-studied K channel subtype involved in smooth muscle relaxation. Because heightened smooth muscle tone may be a causative factor of OAB with DO, increased numbers of Maxi-K channels in the bladder smooth muscle cells associated with effective URO-902 treatment may improve this condition. Based on the favorable safety profile demonstrated in the completed clinical studies in subjects with OAB [REDACTED]

[REDACTED] the current exploratory study is designed to evaluate the efficacy and safety of a single treatment of URO-902 administered via intradetrusor injection in subjects with OAB and UUI.

## 2.3. Benefit/Risk Assessment

### 2.3.1. Potential Benefits

URO-902's mechanism of action has the potential to demonstrate significant therapeutic benefit in the treatment of OAB and UUI. Nonclinical studies conducted with URO-902 have demonstrated no toxicity and no off-target effects in safety pharmacology studies. URO-902 has demonstrated a favorable safety profile in completed clinical studies [REDACTED]

### 2.3.2. Potential Risks

Nonclinical studies evaluating URO-902 support the safety of the doses being evaluated in this study. Data from URO-902 nonclinical studies are summarized in the IB. See [Section 4.3](#) for justification of dose selection.

URO-902 at doses of up to 24 mg (which is the starting dose being evaluated in the current study) administered by direct injections into the bladder wall/detrusor muscle has been evaluated in a previous clinical study ION-03. No clinical safety signals (including no urinary retention), were identified in the studies. More detailed information about the known and reasonably expected adverse events of URO-902 administered via intradetrusor injections can be found in the IB.

The risk to subjects in the current study will be minimized by compliance with the eligibility criteria, proper study design, close monitoring, and an independent Data and Safety Monitoring Board (DSMB). The study follows a dose-escalation design. The DSMB will make recommendations regarding dose escalation only after unblinded review of safety data from all subjects in Cohort 1 up to Week 6.

URO-902 is an investigational drug and should only be used as specified in the clinical study protocol. Subjects should be excluded from treatment with URO-902 in accordance with inclusion/exclusion criteria of the protocol.

### 3. OBJECTIVES AND ENDPOINTS

#### 3.1. Objectives

The objectives of this study are as follows:

- To evaluate the efficacy of a single dose of URO-902 24 mg and 48 mg (administered via intradetrusor injection), compared with placebo, in subjects with OAB and UUI up to 48 weeks post-dose
- To evaluate the safety and tolerability of a single dose of URO-902 24 mg and 48 mg (administered via intradetrusor injection), compared with placebo, in subjects with OAB and UUI up to 48 weeks post-dose

#### 3.2. Endpoints

This exploratory study has no formal statistical primary endpoint hypothesis. Study endpoints are as follows:

##### 3.2.1. Exploratory Efficacy Endpoints

Exploratory efficacy endpoints include the following:

- Change from baseline at Week 12 in average daily number of UUI episodes
- Change from baseline at Week 12 in average daily number of micturitions
- Change from baseline at Week 12 in average daily number of urinary incontinence (UI) episodes
- Change from baseline at Week 12 in average daily number of urgency episodes
- Proportion of subjects achieving  $\geq 50\%$ ,  $\geq 75\%$ , and 100% reduction from baseline at Week 12 in UUI episodes per day
- Change from baseline at Week 12 in average volume voided per micturition
- Health outcomes parameters:
  - Change from baseline at Week 12 in total summary score from the urinary Incontinence-Specific Quality-of-Life Instrument (I-QOL)
  - Change from baseline at Week 12 in OAB Questionnaire (OAB-q) scores
  - Overall change of bladder symptoms based on the Patient Global Impression of Change (PGI-C) scale score at Week 12

- Urodynamic parameters (read by an independent central reviewer):
  - Cystometric volume at 1st sensation to void (FSV)
  - Maximum cystometric capacity (MCC)
  - Maximum detrusor pressure during the storage phase (corrected PdetMaxStorage)
  - Presence/absence of the first involuntary detrusor contraction (IDC) and, if present:
    - Volume at first IDC (Vol@1stIDC)
    - Maximum detrusor pressure during the first IDC (corrected Pdet@1stIDC)

### **3.2.2. Safety Endpoints**

Safety endpoints include adverse events, serious adverse events, physical examination, vital signs (pulse rate, blood pressure, respiration rate, and body temperature), hematology and clinical chemistry, post-void residual (PVR) urine volume, electrocardiograms (ECGs), concomitant medications and concurrent procedures.

### **3.2.3. Other Endpoints**

Other endpoints include *hSlo* cDNA concentrations (blood and urine).

## 4. STUDY DESIGN

### 4.1. Overall Design

This is a multicenter, randomized, double-blind, placebo-controlled, single-treatment, 2 cohort, dose-escalation study evaluating the efficacy and safety of URO-902 (24 mg or 48 mg) in the treatment of OAB and UUI in female subjects aged 40 to 79 years old. Subjects must complete all screening procedures and must meet all eligibility requirements to qualify for enrollment and randomization.

Safety and efficacy assessments and study procedures are outlined in the study schema ([Section 1.2](#)) and the Schedule of Assessments ([Section 1.3](#)).

The total duration of the study is up to 53 weeks including a 5-week screening and randomization period (Days -35 to -1); treatment on Day 1, and a 48-week double-blind post-treatment/follow-up period. Study visits will be identical for Cohorts 1 and 2. Subjects will be evaluated at the Screening Visit (Visit 1) for eligibility. Eligible subjects will be randomized to treatment within each cohort at the Randomization Visit (Visit 2); however, subjects will be administered study treatment via cystoscopy on Day 1 (Visit 3). All subjects will be evaluated at scheduled post-treatment visits at Weeks 2, 6, 12, 18 (phone/virtual), and 24 (Visits 4 to 8, respectively), or until the subject exits the study. Afterwards, for subjects who have completed the Week 24 Visit (Visit 8), 2 follow-up telephone visits (or other virtual technology visits) for assessment of safety will be performed at Week 36 (Visit 9) and Week 48 (Visit 10).

An estimated total of 78 subjects will receive treatment across 2 cohorts ([Section 1.2](#)), with approximately 39 subjects randomized into each cohort. In both cohorts, subjects will be randomized in a 2:1 ratio to receive either URO-902 (24 mg or 48 mg) or placebo. Each cohort will be randomized separately, and enrollment will be sequential, starting with Cohort 1 (URO-902 24 mg [ $n = 26$ ] and placebo [ $n = 13$ ]) and followed by Cohort 2 (URO-902 48 mg [ $n = 26$ ] and placebo [ $n = 13$ ]). Subjects in both Cohort 1 and Cohort 2 will be randomized centrally to receive either a single treatment of URO-902 or matching placebo.

In Cohort 1a, randomization will be stratified by baseline UUI episodes per day (ie,  $\leq 3$  vs.  $> 3$  UUI episodes per day) and presence or absence of DO (as determined by the investigator) at Visit 2. In Cohort 1b and Cohort 2, randomization will be stratified by baseline UUI episodes per day and previous use of onabotulinumtoxinA (naïve vs. prior use). OnabotulinumtoxinA treatment for urological indications must have occurred at least 12 months prior to starting the Screening Bladder Diary. Enrollment for subjects with previous onabotulinumtoxinA use will be capped at 50% of the total subject population per cohort. See details on stratification factors in [Section 6.5](#).

In Cohort 1, an unblinded review of safety data by the DSMB will be performed after all subjects reach Week 6 (or prematurely exited the study prior to Week 6). Randomization into Cohort 2 will begin only after the DSMB has recommended it is safe to proceed. Details on tasks and

responsibilities and assessments of safety parameters will be provided in the DSMB Charter. The independent DSMB will review the safety data throughout the entire study.

For each subject in Cohort 1 or Cohort 2, a single treatment will be administered on Day 1 (Visit 3) after fulfillment of the “day of treatment criteria” ([Section 6.2](#)). Subjects will receive a single treatment of URO-902 or placebo administered by intradetrusor injections via cystoscopy. Details of the study treatment procedure are provided in [Section 6.3](#).

Subjects will be instructed to contact the study site to report any adverse events that occur within 48 hours following administration of study treatment. A 3-day Bladder Diary will be used to collect information to assess exploratory efficacy endpoints related to the number of UUI, micturition, urgency, and UI episodes per day as well as one 24-hr volume voided of urine.

Medications prohibited before and during the study and the associated washout periods as well as permitted medications are described in [Sections 6.9.1](#) and [6.9.2](#), respectively. Starting at Week 24, subjects can request and receive additional OAB treatment(s) at the clinical discretion of the investigator. Subjects who receive additional OAB treatment(s) at Week 24 or after will only be followed to assess adverse events at any future telephone (or other virtual technology) visits (Week 36 and/or Week 48). No efficacy assessments will be performed once a subject receives additional OAB treatment.

#### **4.1.1. Clinical Hypothesis**

Due to the exploratory nature of this trial, there is no formal hypothesis. Statistical testing will be performed to estimate the treatment effect of URO-902 relative to placebo in female subjects with OAB with UUI.

#### **4.2. Scientific Rationale for Study Design**

Study URO-902-2001 is a randomized, double-blind, placebo-controlled, single-treatment, 2 cohort, dose-escalation, exploratory efficacy and safety study.

The dose-escalation design, including interim safety analyses and DSMB review between each cohort, helps minimize the risk to subjects. Randomization into Cohort 2 (higher dose) will begin only after the DSMB has recommended it is safe to proceed.

Randomization will be stratified by baseline UUI episodes per day, presence or absence of DO (as determined by the investigator), and previous use of onabotulinumtoxinA (naïve vs. prior use) to ensure balance across the treatment groups. See details on stratification factors in [Section 6.5](#).

This study is in the early stages of the development program for URO-902. There are no nonclinical studies that have investigated the genotoxic or reproductive effects of URO-902. Therefore, the study only includes female subjects of nonchildbearing potential. The study is randomized and double-blind to minimize investigator and subject bias and will provide a

placebo comparator for evaluating the safety and efficacy of the 2 doses of URO-902 being studied. In addition, relevant safety parameters including adverse events (AEs), SAEs, AEs of urinary retention and UTI as per protocol definition, physical examination, vital signs (pulse rate, blood pressure, respiration rate, and body temperature), urine dipstick reagent strip test, urinalysis/urine culture/sensitivity, as applicable, hematology and clinical chemistry, PVR urine volume, kidney and bladder ultrasound, concomitant medications and concurrent procedures will be closely monitored throughout the study.

#### 4.3. Justification of Dose

An extensive series of *in vitro* and *in vivo* nonclinical studies evaluating the activity and safety of URO-902 have been conducted in OAB and ED animal models at doses up to 1 mg. The results of the nonclinical evaluations supported the initiation of URO-902 clinical studies. No toxicity was observed at any dose level in any of the preclinical studies at any dose in studies conducted to date, including multiple dosing in the ED rat model. Extensive data in the ED and OAB animal models has shown neither histopathological abnormality at any time point in any of 40 organs evaluated or expression of the gene in any other organ other than the organ that underwent transfer more than 1 week after that transfer, as well as in ED studies conducted up to 1 month after transfer.

The bladder preclinical studies evaluated single doses of 0.01, 0.03, 0.1, 0.3, and 1 mg based on an obstructed bladder surface area of 12.56 cm^2 and an average approximate bladder volume of 4 mL. The formula for surface area is  $4\pi r^2$ . Hence, human bladder surface area (average bladder volume of 400 mL) is 263.5 cm^2. Therefore, the approximate dose relationship of human to rat bladder is 20:1. In the completed OAB clinical studies, doses up to 25 mg by direct injection into the bladder wall/detrusor muscle were well-tolerated. Data from completed URO-902 nonclinical and clinical studies are summarized in the IB.

In the [REDACTED]

[REDACTED] No clinically meaningful safety signals were identified at either the 16 mg or 24 mg dose in [REDACTED] A starting dose of 24 mg will be initially tested in the planned Phase 2a clinical study URO-902-2001 to evaluate the safety and efficacy of URO-902 in subjects with OAB and UUI. Study URO-902-2001 has a dose-escalation design. Based on the unblinded review of observed safety data from all subjects in Cohort 1 (URO-902 24 mg) up to Week 6, the DSMB will make the recommendation to proceed with Cohort 2. Randomization into Cohort 2 (URO-902 48 mg) will begin only after the DSMB has recommended it is safe to proceed.

The dose equivalent to the 24 mg human dose and the 48 mg human dose in the rat is no more than 0.480 mg and 0.960 mg, respectively. As described above, the obstructed bladder preclinical studies in the rat evaluated single doses of up to 1 mg based on surface area of the bladder. In the rat ED model, doses up to 1 mg were administered by intracavernous injection. Thus, the starting

dose concentration of URO-902 at 24 mg as well as the highest dose to be evaluated in the planned clinical study (48 mg) are well within the range of doses investigated in the preclinical studies.

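### Section 4.3's rat equivalents for 24 mg and 48 mg contradict its own 20:1 scaling; on its own figures both doses exceed the highest rat dose tested

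*Protocol*

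**What the plan says.** Protocol Section 4.3 (Justification of Dose) makes a three-step argument.

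1. The rat bladder studies used "single doses of 0.01, 0.03, 0.1, 0.3, and 1 mg". The section gives a surface area of 12.56 cm² for the obstructed rat bladder (about 4 mL) and 263.5 cm² for a 400 mL human bladder, with the sphere formula for area. It concludes: "Therefore, the approximate dose relationship of human to rat bladder is 20:1".
2. For 24 mg and 48 mg it then says that the dose equivalent to the "human dose in the rat is no more than 0.480 mg and 0.960 mg, respectively". The next sentence refers back to the surface-area basis of the rat doses, and adds that the rat erectile dysfunction model also went up to 1 mg.
3. It concludes that the starting dose and the highest dose "are well within the range of doses investigated in the preclinical studies".

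Section 2.3.2 (Potential Risks) says: "Nonclinical studies evaluating URO-902 support the safety of the doses being evaluated in this study". It sends the reader to Section 4.3 for the dose selection.

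**The concern.** Steps 1 and 2 cannot both be right. If a human dose is about 20 times its rat equivalent, the equivalent of 24 mg is above 1 mg, not below half of it. The claim in step 3 depends entirely on the step 2 figures.

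The matter weighs most for 48 mg. The readable text reports human intradetrusor experience only up to 24 mg (Section 2.3.2) or 25 mg (Section 4.3). For 48 mg, the rat comparison is therefore the main quantitative support that a reader of the public text can see. Section 4.2 adds that genotoxic and reproductive effects have not been studied nonclinically, so the coverage that is claimed should be stated correctly. An ethics committee or investigator reading Section 4.3 would take both doses to be covered by the rat studies when the section's own numbers say otherwise.

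**Working it through.** **Inputs (all from Protocol Section 4.3, none redacted).** Human bladder area 263.5 cm² at 400 mL; rat bladder area 12.56 cm² at about 4 mL; stated ratio 20:1; top rat dose 1 mg; stated rat equivalents 0.480 mg and 0.960 mg.

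**The plan's ratio reproduces approximately.** 263.5 / 12.56 = 20.98. Exact spheres of 400 mL and 4 mL have areas of 262.5 and 12.19 cm², a ratio of 21.54. The stated 20:1 is a rounded-down version of these.

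**The plan's equivalents do not reproduce.** The formula is rat equivalent = human dose / ratio.

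| Ratio used | 24 mg | 48 mg | Human dose matching 1 mg in the rat |
|---|---|---|---|
| 20 (as stated) | 1.20 mg | 2.40 mg | 20 mg |
| 20.98 (stated areas) | 1.14 mg | 2.29 mg | 21.0 mg |
| 21.54 (exact spheres) | 1.11 mg | 2.23 mg | 21.5 mg |
| 100 (volumes, 400/4) | 0.24 mg | 0.48 mg | 100 mg |
| 50 (implied by the printed values) | 0.480 mg | 0.960 mg | 50 mg |

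The implied ratio is 24 / 0.480 = 48 / 0.960 = 50. Neither document mentions 50:1. Every surface-area version puts both doses above 1 mg. A volume ratio would put them below, but it is not the protocol's method and does not give the printed pair either.

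**Size of the error.** 50 / 20 = 2.5 and 50 / 20.98 = 2.4, so the printed equivalents are too low by a factor of about 2.4 to 2.5 (2.3 with exact spheres, 50 / 21.54).

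**Cross-check per unit area.** The top rat dose is 1 / 12.56 = 0.080 mg/cm². The human doses are 24 / 263.5 = 0.091 and 48 / 263.5 = 0.182 mg/cm². Both are higher than the rat value, by 1.14 and 2.29 times.

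**Possible origin.** 24 × 20 = 480 and 48 × 20 = 960, so the digits fit multiplication by 20 with the result read as micrograms. This is an inference, and nothing here depends on it.

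**The case against.** The arithmetic itself is hard to contest. Setting an upper bound does not rescue the printed figures, because the recomputed values lie above it. The section speaks of a dose concentration, but it gives no rat concentration or injection volume, and the comparison is in mg. The redactions do not touch the areas, the ratio, the equivalents or the conclusion. The real objections concern consequence.

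- **24 mg is a marginal case.** The ratio is called approximate, and the excess over 1 mg is only 11% to 20%. Holding the rat area fixed, a human bladder of 400 × (24/20.98)^1.5 ≈ 490 mL would bring 24 mg down to 1 mg. That dose also has direct human support. This stands: correcting the figure barely changes the case for 24 mg, although it would still not be well within the range. It does not help 48 mg, which would need 400 × (48/20.98)^1.5 ≈ 1,380 mL.
- **Other safeguards exist.** Section 4.3 reports no toxicity at any dose tested, and escalation waits for the DSMB's review of observed Cohort 1 safety data to Week 6. This stands as far as it goes. Exceeding the top rat dose crosses no known toxic threshold; what is lost is the claim of coverage. Nothing in the documents says that the DSMB uses the rat margin, so any reliance on it by the DSMB is an inference.
- **Fuller support may lie elsewhere.** The Investigator's Brochure and the redacted text cannot be seen, so the weight of the rat margin in the whole file is unknown. That is fair, but it does not make the printed statement correct.
- **Section 2.3.2 is not shown to be false.** Its sentence is qualitative and refers to the Brochure for the data. It needs a check, because it points to Section 4.3, but not necessarily a rewrite.

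**Conclusion.** The concern holds. On the protocol's own surface-area scaling, 24 mg corresponds to 1.14 to 1.20 mg in the rat and 48 mg to 2.29 to 2.40 mg, against a highest tested dose of 1 mg. Section 4.3 places the two doses at 0.48 and 0.96 times the top rat dose. Even at face value, 0.96 leaves a margin of only 4%, which is hardly well within the range.

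The result rests on the protocol's own areas, its choice of surface area as the basis, and its list of rat doses; it needs no outside figure. It says nothing about whether either dose is safe, and it leaves the endpoints, sample size and analyses untouched. It must still be fixed, because a wrong safety-margin figure supports a dose that is about twice the readable human experience.

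**What to change.** - In Section 4.3, recompute the rat equivalents from the stated surface-area ratio, or state and justify the different ratio that was used.
- Correct or withdraw the sentence that both doses are well within the preclinical range. If the 20:1 ratio stands, say plainly that both doses exceed the top rat dose, and by how much, and set out what other evidence supports 48 mg.
- Check that the nonclinical safety statement in Section 2.3.2 is still adequately supported, and align it with the corrected section.
- Send the reconciled figures to the ethics committees, the investigators and the DSMB.

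The cost is a wording correction and a notification. No new data are needed, but the stated nonclinical margin becomes less favourable. The choice of dose remains with the sponsor, and none is proposed here.
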